10.3.2 Reporting Serious Adverse Events to Regulatory Agencies

The Sponsor will determine which SAEs qualify for expedited reporting to regulatory agencies. SAEs that qualify for expedited reporting will be submitted to regulatory agencies in accordance with applicable federal regulations.

10.4 Follow-up of Adverse Events and Laboratory Test Abnormalities

Adverse event information will be collected during the clinical trial from the time the subject signs informed consent through the final study visit. SAEs that are considered related to study drug by the Investigator or Sponsor should be followed until the events resolve or stabilize.

10.5 Pregnancy Reporting

10.5.1 Definition of Female of Childbearing Potential

For purposes of this study, all female subjects are considered of childbearing potential.

10.5.2 Testing and Acceptable Methods of Birth Control

Females must agree to periodic pregnancy testing and use a medically acceptable method of contraception while receiving protocol-assigned study drug. Refer to [Section 6.14.1](#) for additional information.

10.5.3 Time Period for Collecting Pregnancy Information

Females of child bearing potential should be instructed to contact the Investigator immediately if they suspect they might be pregnant (e.g., missed or late menstrual period). If a subject or Investigator suspects that a subject may be pregnant at any time during the study, the investigational product must be withheld until the results of laboratory pregnancy testing are available. If pregnancy is confirmed, the subject must not receive or apply further investigational product and must be discontinued from the study.

10.5.4 Action to be Taken if Pregnancy Occurs

If following initiation of investigational product, it is subsequently discovered that a trial subject was pregnant or may have been pregnant at the time of investigational product exposure, the Investigator must immediately notify the Medical Monitor of this event and record the pregnancy on the appropriate pregnancy surveillance form. The form will be sent to the Medical Monitor by fax to [name] or email at [contact]. The Investigator must notify the IRB of any pregnancy associated with the study therapy and keep careful source documentation of the event.

Protocol-required procedures for those subjects that are discontinued from the study must be performed on the subject unless contraindicated by pregnancy (e.g., x-ray studies). Other appropriate pregnancy follow-up procedures should be considered if indicated, including counseling of the subject by the Investigator and her managing physician or health care provider (e.g., obstetrician). In addition, the Investigator must report to the Medical Monitor, on the appropriate pregnancy surveillance form(s), any follow-up information regarding the course of the pregnancy, including perinatal (period immediately before and after birth) and neonatal (infants up to 28 days after birth) outcome.

Although pregnancy itself is not an AE, any complications during pregnancy should be recorded as AEs (or SAEs – if they fulfill the SAE criteria). **Offspring will be followed for a minimum of eight weeks.** Any congenital anomaly/birth defect in a child born to a subject exposed to the test article(s) will be recorded as a SAE and details documented in the pregnancy surveillance form. An abortion, whether accidental, therapeutic or spontaneous will be reported as a SAE.

11 DATA ANALYSIS AND STATISTICAL METHODS

11.1 Sample Size Determination

A sample size of twenty-four (24) subjects is based on the maximum planned enrollment under Study BBI-4000-CL-105.

11.2 Analysis Populations

Two populations will be used for analysis: Safety and PK. The definition of these two populations follows:

- **Safety Population:** All enrolled subjects who applied at least one dose of study drug and have at least one post-baseline safety assessment.
- **Pharmacokinetic Population:** All enrolled subjects who applied at least one dose of study drug and have at least one quantifiable PK sample for analysis.

11.3 Statistical Analysis

11.3.1 General Statistical Methodology

- Baseline is defined as the last assessment prior to the first application of study drug on Day 1 under Study BBI-4000-CL-105.
- All statistical processing will be performed using Statistical Analysis System (SAS[®]) unless otherwise stated.
- Continuous data will be summarized using descriptive statistics (number of values, mean, standard deviation, median, minimum and maximum). Categorical data will be summarized using frequency tables (frequencies and percent).
- A SAP, describing all statistical analyses will be provided as a separate document. The SAP will be finalized prior to locking the database. The SAP will contain any modifications to the analysis plan presented below.

11.3.2 Demographics, Baseline Characteristics, Medical History, Hyperhidrosis History, and Concomitant Medications

Demographic data, baseline characteristics, medical history including history of axillary hyperhidrosis, and prior and concomitant medications will be summarized using descriptive statistics.

11.3.3 Treatment Compliance

The subject or parent(s)/guardian(s) will record the date and time of all applications made to the right and left axilla or missed applications in the dosing diary card. Subject compliance during the overall treatment period and by visit will be summarized.

11.3.4 Drug Exposure

Amount of study drug (weight) and the number of days of study drug application will be summarized.

11.4 Primary Analysis

11.4.1 Safety

Safety evaluations will consist of AEs, local application site tolerability, vital signs, laboratory measurements (hematology, chemistry, and urinalysis, and pregnancy testing), ECGs and physical examinations. Full details will be specified in the SAP. A general description of the planned analysis is as follows:

- Adverse Events:
 - Adverse events will be descriptions will be mapped to standard terms, i.e., MedDRA System Organ Class and Preferred Term.
 - Adverse events that occurred during the screening period will be listed separately and will not be included in the AE tabulations.
 - Adverse events that start on or after first dose will be considered a TEAE. At each post-baseline visit, the number and proportion of subjects reporting any given TEAE will be tabulated by severity; each subject will be counted only once according to the worst severity reported up to the current visit. Separate tables will be constructed for (a) all reported TEAEs, (b) protocol treatment related TEAEs, (c) serious TEAEs, and (d) TEAEs leading to protocol treatment discontinuation.
- At each visit, local tolerability (burning, itching, stinging, scaling, and erythema at either axilla) will be described by severity as defined in [Appendix F](#).
- Vital signs will be summarized similarly as for laboratory parameters but without shift tables.
- Laboratory parameters will be descriptively summarized (mean, SD, median, minimum, maximum) for values at each visit and for changes from baseline at each subsequent visit. In addition, at each post baseline visit, parameter status (low, normal, high) will also be summarized as shift tables vs. baseline status.
- Descriptive statistics and/or frequency tables will be prepared as appropriate for physical examinations, and ECG (HR, RR, QTcF, PR, and QRS) parameters
- Concomitant medications will be mapped according to the World Health Organization Drug Dictionary and will be presented in data listings.

11.4.2 Pharmacokinetics

Plasma concentrations of sofpironium and BBI-4010, will be determined using validated liquid chromatography with tandem mass spectrometry (LC-MS/MS) analytical methods. The lower limit of quantification (LLQ) of the assay in plasma is 0.0555 ng/mL for both sofpironium and BBI-4010. Specifics of the analytical procedures will be provided in separate bioanalytical documentation.

Individual plasma C_{trough} values of sofpironium and BBI-4010 will be summarized descriptively using the arithmetic mean, SD, CV (%), median, minimum and maximum. Mean (\pm SD) C_{trough} values will also be presented graphically by week to assess exposure, accumulation and steady state

Additional details regarding PK analysis will be provided in the SAP.

11.5 Exploratory Analysis

- Descriptive summaries will be provided for HDSM-Ax and HDSM-Ax, Child, Summary Questions (No. 4 and No. 5) and PGI-S. Mean changes from baseline and observed values will be summarized by time point. The SAP will contain full details.
- For HDSM-Ax and HDSM-Ax, Child, the mean of the items in Section No. 1, No. 2, and No. 3 will be calculated for every subject at each time point. The mean will be derived by taking the total score and dividing it by the number of questions answered. Subjects must answer ≥ 6 of the 11 sub-items to be evaluable for HDSM-Ax or HDSM-Ax, Child total score. Observed values and changes from baseline at each time point will be summarized and plotted over time using descriptive statistics.
- For the HDSM-Ax or HDSM-Ax, Child Summary Questions (No. 4 and No. 5), the score for each question, will be reported for every subject at every visit and summarized and plotted over time using descriptive statistics.
- For PGI-S, the score will be reported for every subject at every visit and summarized and plotted over time using descriptive statistics.
- For PGI-C, the score will be reported for every subject at Week 12 and Week 24 (EOT) and summarized and plotted over time using descriptive statistics.

Missing data will not be imputed for any analyses.

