APPENDIX A HDSM-AX, CHILD (≥9 TO <12 YEARS OF AGE)

HDSM-AX CHILD (VERSION 28 FEB 2018)

INSTRUCTIONS: We are interested in finding out about your **underarm** sweating.

- Circle the best answer to each question.
 - Think about sweating in your **underarms only**.
 - Think about your sweating **this morning and yesterday**.
- Please answer **ALL** questions.

1. Since you woke up yesterday, how often did you have these things?

	None of the time	A little of the time	Some of the time	Most of the time	All of the time
a) Damp or wet clothes from underarm sweating ?	0	1	2	3	4
b) Underarm sweating for no reason?	0	1	2	3	4

2. Since you woke up yesterday, how much did you have these things?

	I did not have this	A tiny amount	A little	A lot	A great amount
a) Underarm sweating when you felt nervous, scared, or worried?	0	1	2	3	4
b) Damp or wet clothing from underarm sweating ?	0	1	2	3	4
c) Underarm sweating after sitting quietly?	0	1	2	3	4
d) Underarm wetness?	0	1	2	3	4
e) Underarm sweating for no reason?	0	1	2	3	4
f) Underarm sweating that you could not hide?	0	1	2	3	4
g) Underarm sweating when you were not hot?	0	1	2	3	4

PROPRIETARY AND CONFIDENTIAL

3. Since you woke up yesterday, how much did you want to do these things?

	Not at all	A tiny amount	A little	A lot	A great amount
a) Change clothes because of underarm sweating ?	0	1	2	3	4
b) Wipe sweat from your underarms ?	0	1	2	3	4

4. Since you woke up yesterday, how much of the time did you have underarm sweating?

- 0 None of the time
- 1 A little of the time
- 2 Some of the time
- 3 Most of the time
- 4 All of the time

5. Describe your underarm sweating AT ITS WORST since you woke up yesterday?

- 0 I did not have underarm sweating
- 1 I had a tiny amount of underarm sweating
- 2 I had some underarm sweating
- 3 I had a lot of underarm sweating
- 4 I had a great amount of underarm sweating

6. Patient Global Impression of Severity (PGI-S)

Please choose the response below that best describes the severity of your underarm sweating over the past week.

- None
- Mild
- Moderate
- Severe
- Very severe

7. Patient Global Impression of Change (PGI-C)

Please choose the response below that best describes the overall change in your underarm sweating since you started taking the study medication.

- Very much better
- Moderately better
- A little better
- No change
- A little worse
- Moderately worse
- Very much worse

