### 12.3 General Considerations for Analysis

#### 12.3.1 Safety and Efficacy Analysis

- The Safety population will be used for evaluation of safety and efficacy parameters.
- Analyses of safety and efficacy data will be performed in Statistical Analysis System (SAS) software version 9.2 or higher (SAS Institute Inc., 2008).
- The final analysis will be conducted after all subjects have completed the study and the database is locked. Listings will report all data collected in the database.
- If a data table is sparse, only a listing will be presented. Unless otherwise stated, all listings will be sorted by subject number and visit date. Continuous variables will generally be summarized using means, medians, standard deviation (SD), minimum, and maximum. Discrete variables will be summarized by frequency and percentages.
- Summary tables will indicate the number of subjects with complete data for each measurement, event, or outcome.
- Data will be summarized in plots organized by time point and over time.
- For multiple or repeated assessments for the same visit, the latest assessment will be included in the summary tables.
- Summary tables will only include data from scheduled visits.
- Data from unscheduled visits will be included in the listings.
- If additional analyses are required to supplement the planned analyses, they may be performed and will be identified in the appropriate section of the clinical study report

(CSR). Any substantial deviations from the planned SAP will be updated in the SAP and approved.

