# 13 STATISTICAL ANALYSIS

## 13.1 Baseline Parameters, Demographics, Medical History, Hyperhidrosis History, Concomitant Medications, Disposition and Drug/Alcohol Screening, and Pregnancy Testing

- The total number of subjects enrolled in the study.
- Subject demographics and baseline characteristics will include, date of birth, gender, race, ethnicity, height and weight, and age at onset and duration of hyperhidrosis, will be summarized and listed. Descriptive statistics (mean, SD, median, minimum, and maximum for numerical variables; count and percentage for categorical variables) will be presented where applicable.

- Subject medical, hyperhidrosis and medication history will be listed by MedDRA system organ class and preferred term (PT). A listing sorted by subject number, MedDRA system organ class and PT, and onset date will also be presented.
- Subject medication history will be mapped according to the WHODD.
- A listing of subject disposition will include start date and time of first study drug application in the extension study.
- The number of subjects who complete treatment (Day 168 [ $\pm 5$  days], EOT) will be summarized and listed.
- The number of subjects who complete study (Day 182 [ $\pm 5$  days], EOS) will be summarized and listed.
- The number of subjects who prematurely discontinue from the study and reason for discontinuation will be summarized and listed. The number of subjects who prematurely withdraw from study drug but remaining in the study will be summarized.
- Concomitant medications (start date on or after Day 1 of Study BBI-4000-CL-105) will be summarized using descriptive statistics.
- Use of concomitant medications (chronic medications or as needed medications e.g., acetaminophen, EMLA cream) are permitted during the screening and active study period (Day 1 through Day 168 [ $\pm 5$  days]) and will be recorded on the eCRF.
- Changes in concomitant medication usage will be recorded on the eCRF. If the reason for change is related to an AE, the event will be recorded in as an AE in the eCRF.
- Concomitant medications will be mapped according to the WHODD and will be presented in data listings.
- Drug and alcohol screen by visit will be listed.
- Pregnancy test (positive or negative) by visit will be listed.

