#### **Efficacy Figures – Safety Population**

- Figure 14.2.1 Mean Changes from Baseline Over Time in HDSM-Ax, Child and HDSM-Ax (All)
- Figure 14.2.2 Mean Observed Values over Time in HDSM-Ax, Child and HDSM-Ax (All)
- Figure 14.2.3 Mean Changes from Baseline Over Time in HDSM-Ax, Child and HDSM-Ax Anchors (All)
- Figure 14.2.4 Mean Observed Values over Time in HDSM-Ax, Child and HDSM-Ax Anchors (All)
- Figure 14.2.5 Mean Changes from Baseline Over Time in PGI-S (All)
- Figure 14.2.6 Mean Observed Values over Time in PGI-S (All)
- Figure 14.2.7 Mean Changes from Baseline Over Time in PGI-C (All)
- Figure 14.2.8 Mean Observed Values over Time in PGI-C (All)

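### PGI-C and PGI-S have no numeric code, yet SAP Appendix A plans mean plots of both and names no table counting how many subjects improved or worsened

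*Protocol*

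**What the plan says.** **The instruments.** Items 6 and 7 of both questionnaires (Protocol Appendices A and B, SAP Appendices C and D) are PGI-S and PGI-C. PGI-S asks: "Please choose the response below that best describes the severity of your underarm sweating over the past week". It offers five labels from none to very severe. PGI-C asks: "Please choose the response below that best describes the overall change in your underarm sweating since you started taking the study medication". It offers seven labels: three better, one no change, three worse. No numbers are printed beside either set. HDSM-Ax items 1 to 5, on the same forms, carry printed values 0 to 4.

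**The analysis text.** Protocol 11.5 and SAP 13.4 call both items a score. For PGI-S they specify mean changes from baseline. For PGI-C the Protocol says "For PGI-C, the score will be reported for every subject at Week 12 and Week 24 (EOT) and summarized and plotted over time". The rest of that sentence refers only to descriptive statistics.

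**The planned outputs (SAP Appendix A).** The figures include "Mean Observed Values over Time in PGI-S (All" and "Mean Observed Values over Time in PGI-C (All", each with a companion figure of mean changes from baseline. Tables 14.2.3 and 14.2.4 summarise the score and its change from baseline. No category-count or shift table is named for either item. PGI-S has a named listing (16.2.6.2). PGI-C has none.

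**The general rules.** Protocol 11.3.1: "Categorical data will be summarized using frequency tables (frequencies and percent". SAP 12.3.1: "Discrete variables will be summarized by frequency and percentages".

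**The concern.** One exploratory objective is to assess the effect on PGI-C, another the effect on PGI-S. A mean of worded grades needs a numeric code, and here the code, its spacing and its direction are all left to whoever programs the table. PGI-C is also two-sided, so better and worse grades offset each other in a mean. The simple clinical reading of a long open-label extension is how many children said they were better and how many said they were worse. No named output gives that.

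The plan treats a comparable scale differently. Local tolerability is also an ordered scale, with printed codes 0 to 4, and SAP 13.3.1 gives it the count and percentage of subjects at each severity. The two items without codes are the ones shown as means.

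**Working it through.** The documents state no figure for these endpoints, so there is nothing to reproduce. The check asks what a mean can and cannot show.

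**Inputs**
- n = 24, the maximum enrolment (Protocol 11.1).
- PGI-C code: not in the documents. Assumed +3 (very much better) through 0 (no change) to -3 (very much worse).
- PGI-S code: not in the documents. Assumed 0 (none) to 4 (very severe).
- All distributions are hypothetical.

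**Step 1: different PGI-C results with one mean.** Mean = sum of (count × code) / 24.

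| Distribution | Mean | SD | Median | Minimum | Number worse |
|---|---|---|---|---|---|
| 24 a little better | (24×1)/24 = +1.0 | 0 | +1 | +1 | 0 (0%) |
| 18 moderately better, 6 moderately worse | (36-12)/24 = +1.0 | 1.77 | +2 | -2 | 6 (25%) |
| 16 moderately better, 8 a little worse | (32-8)/24 = +1.0 | 1.44 | +2 | -1 | 8 (33.3%) |
| 12 very much better, 12 a little worse | (36-12)/24 = +1.0 | 2.04 | +1 | -1 | 12 (50%) |

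The plotted mean is the same in all four rows. The minimum shows that at least one subject worsened in the last three, but not how many: the last two rows share both mean and minimum with 8 and 12 worse.

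**Step 2: dependence on the code.** With a reversed 1 to 7 code (new value = 4 minus old value), the same four distributions all have mean 4 - 1 = 3.0. The printed result could be +1.0 or 3.0 for the same answers, and the plan does not say which, or which direction is favourable.

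**Step 3: PGI-S.** A mean change of -1.0 arises from
- 24 subjects at -1;
- 18 at -2 and 6 at +2: (-36+12)/24;
- 16 at -2 and 8 at +1: (-32+8)/24.

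The number worse is 0, 6 or 8.

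**Step 4: change from baseline for PGI-C.** Protocol 6.11 and the Schedule of Activities collect PGI-C at Weeks 12 and 24 only, and the question itself rates change since starting treatment. There is no baseline value. The change-from-baseline part of Table 14.2.4, and Figure 14.2.7, cannot be produced as titled.

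**The case against.** A reader might infer three stronger things. The documents do not support them.

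*That the Protocol prescribes a mean for PGI-C.* The Protocol 11.5 sentence does not use the word, and the mean-change sentence there names PGI-S. SAP 13.1, writing about demographics, takes descriptive statistics to include "count and percentage for categorical variables". For PGI-C the mean rests on the SAP figure titles.

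*That worsening would be hidden.* The default continuous summary includes median, SD, minimum and maximum. Take 20 moderately better with 4 very much worse, against 20 a little better with 4 moderately better. Both have mean 28/24 = +1.17, but median, SD and minimum are +2, 1.90 and -3 in the first and +1, 0.38 and +1 in the second. A table with the default statistics separates them at once. SAP 12.3.1 also has listings report all collected data, and with at most 24 subjects a reader could count by hand.

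*That the plan breaks its own rule.* Neither document classes the PGI items as categorical. If they are categorical, the general rules already require frequencies, and Tables 14.2.3 and 14.2.4 do not exclude them. Appendix A is headed preliminary, so a missing title is weak evidence that an analysis is missing.

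These arguments limit the point but do not remove it. The code is undefined everywhere, the named figures are means, and nothing named gives the number who worsened. A choice among worded labels is categorical on any ordinary reading, so the outputs sit poorly with the general rules even if they do not flatly contradict them.

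**Conclusion.** The point holds as a gap in specification and presentation. PGI-S and PGI-C have no code or direction, means are planned for both, and no category-count table is named. Under the assumed +3 to -3 code with all 24 subjects responding, a PGI-C mean of +1.0 leaves the number worse anywhere among 0, 6, 8 and 12 in the examples worked. Other codes would change the mean but not the ambiguity.

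What is lost from the named tables and figures is the number and percentage who worsened, not the fact that someone did, and not the individual data. The endpoints are exploratory, descriptive and untested, so no inference is at risk. The planned change from baseline for PGI-C is a plain error in the output list, since no baseline exists. The change is worth making because it is cheap and needs no new data.

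**What to change.** Edit SAP 13.4 and Appendix A. Protocol 11.3.1 lets the SAP carry modifications to the analysis, so no protocol amendment is needed.

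- **PGI-C:** report n (%) in each of the seven categories at Weeks 12 and 24, with the number and percentage in any better grade and in any worse grade, in place of the mean figures. A bar chart of the category percentages would keep the commitment to plot the item.
- **PGI-S:** report n (%) per category at each visit and a baseline-by-Week 24 shift table. Keep mean change as a supplement, with its coding and direction stated.
- **Listing:** name a PGI-C listing.
- **Correction:** drop change from baseline from Table 14.2.4 and delete Figure 14.2.7.

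Exact confidence intervals (for example 9.8% to 46.7% for 6 of 24) and a responder cut are optional. The plan's rules do not call for them.

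Cost: SAP wording and about three small tables of extra programming.
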